8.3.1 PREGNANCY FOLLOW-UP

Every female participant will take a pregnancy test on Day 1 of Stimulation. If, after testing negative at Day 1 of Stimulation (meeting inclusion criteria), a participant reports becoming pregnant during the course of the study, she will be withdrawn from further participation. There are no plans to follow participants who become pregnant while enrolled in the study.

9 DATA AND SAFETY MONITORING

9.1 [name] LAB MONITORING PLAN

The purpose of this monitoring plan is to present the [name] Lab's approach to monitoring clinical trials. The plan facilitates compliance with good clinical practice (GCP):

- a. The rights and well-being of human subjects are protected.
- b. The reported trial data are accurate, complete, and verifiable from source documents
- c. The conduct of the trial is in compliance with the currently approved protocol/amendment(s) with GCP, and with applicable regulatory requirement(s)

This section identifies key monitoring activities and specifies the data to be reviewed over the course of a clinical trial. This is a single site, investigator-initiated, clinical trial, so there will be no site monitoring plan in place.

The latest version of the approved IRB application for this clinical trial will be followed at all times. This responsibility falls into the hands of the study coordinator and research assistants. If at any time there is a deviation from protocol, the deviation from protocol log will be filled out. All team members will be trained on how and when to use this log. The most up-to-date IRB application will be on file in the Clinical Trials office in [name]. Deviations will be sent to the IRB every 4-6 weeks (if necessary).

Periodically, study staff should review 3 randomly selected informed consent forms to ensure that (1) these forms have been filled out appropriately, and (2) the consent form process was followed and properly documented. Should any consent form be in violation, the research team will perform and document a complete review of all consent forms.

AE and SAE are clearly defined in this document. Documents of AE and SAE can be found in the study binder on file in the Clinical Trials office in [name]. It is the responsibility of the study coordinator to report all events to the PI in a timely manner (see *9.3 Reporting Procedures*). All AEs and SAEs will be discussed with the PI. For our practices, we have adapted the decision tree provided by the UNC-CH IRB to assist with reporting of such events.

9.2 SAFETY OVERSIGHT

Safety oversight will be under the direction of the PI, who will review AEs in real time and make decisions regarding a participant's continuation of the clinical trial.

9.3 EARLY WITHDRAWAL OF PARTICIPANTS

9.3.1 REASONS FOR WITHDRAWAL

A study participant will be discontinued from further participation if:

- The participant fails to adhere to rules, including stress, exercise, and sleep restrictions
- The participant meets any exclusion criteria (either newly developed or not previously recognized).
- Anything that, in the opinion of the investigator, would place the participant at increased risk or preclude the participant's full compliance with or completion of the study.

Participants are free to withdraw from participation in the study at any time upon request.

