3.2 EXCLUSION CRITERIA

A potential participant who meets any of the following criteria will be excluded from participation in the study:

- Diagnosis of eating disorder (current or within the past 6 months)
- Diagnosis of OCD (lifetime)
- ADHD (currently under treatment)
- Neurological disorders and conditions, including, but not limited to:
 - History of epilepsy
 - Seizures (except childhood febrile seizures and ECT-induced seizures)
 - Dementia
 - History of stroke
 - Parkinson's disease
 - Multiple sclerosis
 - Cerebral aneurysm
 - Brain tumors
- Medical or neurological illness or treatment for a medical disorder that could interfere with study participation (e.g., unstable cardiac disease, HIV/AIDS, malignancy, liver or renal impairment)
- Prior brain surgery
- Any brain devices/implants, including cochlear implants and aneurysm clips
- Traumatic brain injury
- (For females) Pregnancy or breast feeding
- Personal or family history of mental/psychiatric disorder (e.g., anxiety, major depressive disorder, schizophrenia, etc.)
- Diagnosis of an autoimmune disorder
- Failure to pass a urinary drug test at the first session.
- Anything that, in the opinion of the investigator, would place the participant at increased risk or preclude the participant's full compliance with or completion of the study

Justifications for any exclusions based on race, gender, or ethnicity: Non-English speaking individuals are excluded because the ability to accurately and completely communicate study information, answer questions about the study, and obtain consent are necessary.

Justification for excluding women or women who become pregnant: Pregnant participants will be excluded despite the fact that theoretical risk to mother or fetus is exceedingly small, since no safety data for pregnancy is known to exist for tDCS/tACS studies. We will verify pregnancy status via a urine pregnancy test for all female participants prior to receiving treatment on Day 1 of Stimulation.

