5.1 SCREENING

The screening process will involve a telephone call with the potential participant to inform of expectations and determine eligibility. A researcher will conduct a screening with each participant prior to scheduling the first session. If a participant is determined to be ineligible, data from the screening will be retained.

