5.2 STIMULATION SESSIONS

Participants will undergo two sessions with the same procedure; the only change will be the stimulation condition.

5.4.1 SESSION 1

In the initial session, participants will be explained the procedure and reminded of their expectations and rights (informed consent). After obtaining consent, a urine drug test and pregnancy screening will be administered. Once they are both determined to be negative, the stimulation, EEG, and heart rate electrodes will be applied. Participants will then undergo a ten-minute resting state block to record EEG activity. Participants then provide a baseline saliva sample and receive 40 minutes of either 10Hz tACS or sham stimulation (depending on the randomized condition) while watching the 'Reefscape' video. After the stimulation, the participant will complete the stimulation adverse effects questionnaire, and will then provide a final saliva sample. The study coordinator will remove all equipment, and the participant will fill out the final two questionnaires and receive \$20 in compensation.

5.4.2 SESSION 2

The procedure for the second session will follow the same timeline as the first, with the exclusion of informed consent, urine drug test, and pregnancy screening processes. Participants will receive \$40 in compensation at the end of this session.

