10.1 SAFETY PARAMETERS

STIMULATION SIDE EFFECTS. A stimulation adverse effects questionnaire used in previous studies will be administered at the end of each stimulation session. This questionnaire will be used as a safety measure and to collect data on participant experience. The adverse effects questionnaire asks participants to respond on a 4 point Likert scale on the severity of symptoms experienced during the stimulation session (1 = absent, 2 = mild, 3 = moderate, 4 = severe). The side effects listed are headache, neck pain, scalp pain, tingling, itching, ringing/buzzing noise, burning sensation, local redness, sleepiness, trouble concentrating, improved mood, worsening of mood, dizziness, flickering lights, and other (specify). Participants are also asked to rate on a 5 point Likert scale how related they believe the side effects to be to stimulation (1 = no relation, 2 = remote, 3 = possible, 4 = probable, 5 = definite).

In addition to this survey, the study coordinator or research assistant will periodically check in with the participant during the stimulation session to assess side effects.

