10.2 METHODS AND TIMING FOR ASSESSING, RECORDING, AND ANALYZING SAFETY PARAMETERS

10.2.1 ADVERSE EVENTS

All AEs, including local and systemic reactions not meeting the criteria for “serious adverse events”, will be captured on the appropriate CRF. In addition, the AE Report Form will be completed by the study coordinator (Appendix B). The AE Report Form includes the following:

- What is known about the therapy
- What is known about previous reported side effects
- If the AE occurred in temporal relation to the therapy
- Whether or not the AE improves or disappears when treatment is stopped
- Whether the AE is worsening of baseline symptoms
- Whether the AE is related to concurrent medical condition or medication use

Once complete, this form will be given to the PI and Co-I, who will review, comment, and sign this form. Completed forms will be placed in the participant’s folder.

In addition, the study coordinator will document any AE occurrence on the AE log (*Appendix D*), which includes information such as the date of the AE, severity, relationship to the treatment (assessed by the PI and Co-I*), actions taken, and outcome(s). The log will be reviewed and initialed by the PI 72 hours after being completed. All AEs occurring during the clinical trial will be documented appropriately regardless of relationship to tACS. All AEs will be followed to adequate resolution and will be graded for severity and relationship to study treatment. Any medical condition noted at the initial session will be considered at baseline and not reported as an AE.

All AEs will be graded for severity using the following guidelines:

- **ASYMPTOMATIC.** The participant is exhibiting no symptoms due to this event; no treatment needed.
- **MILD.** Event results in mild or transient discomfort, not requiring intervention or treatment; does not limit or interfere with daily activities (e.g., insomnia, mild headache)
- **MODERATE.** Event is sufficiently discomforting so as to limit or interfere with daily activities; may require interventional treatment (e.g., fever requiring antipyretic medication). In the case of a moderate AE, the medical advisor may recommend an over the counter medication.
- **SEVERE AND UNDESIRABLE.** Event results in significant symptoms that prevent normal daily activities; may require hospitalization or invasive intervention (e.g., anemia resulting in blood transfusion).

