10.4 TYPES AND DURATION OF FOLLOW-UP OF PARTICIPANTS AFTER ADVERSE EVENTS

The study coordinator will follow up within one week of an adverse event.

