APPENDIX A: SCHEDULE OF EVENTS

	Phone Screening	Day 1 of Stimulation	Day 2 of Stimulation
Procedures			
Provide Verbal Consent	x		
Signed Consent Form		x	
Assessment of Eligibility Criteria	x	x	
Urine Pregnancy Test		x	
Urine Drug Test		x	
Baseline Assessments (PSS, CD-RISQ, PSQI)		x	
Saliva Sample		x	x
Stimulation		x	x
Stimulation Questionnaire		x	x
Saliva Sample		x	x
Final Questionnaires (PANAS, STAI)		x	x

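### No scheduled step before the second stimulation re-checks exclusions or asks about adverse events since session 1, and no contact is scheduled after visit 2, so two of the protocol's rules rely on spontaneous reporting

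*Combined protocol and SAP*

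**What the plan says.** **The two rules.** Section 9.3.1 gives as a reason for discontinuing a participant: "The participant meets any exclusion criteria (either newly developed or not previously recognized". Section 10.2.1 (Adverse Events) states: "All AEs occurring during the clinical trial will be documented appropriately regardless of relationship to tACS". Neither is limited to events that a participant chooses to mention.

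**Eligibility.** Section 5.1 places screening once, at the start: "A researcher will conduct a screening with each participant prior to scheduling the first session". In Appendix A the row "Assessment of Eligibility Criteria" is marked for the phone screen and Day 1, and is blank for Day 2. Section 5.4.2 says that session 2 follows the session 1 timeline "with the exclusion of informed consent, urine drug test, and pregnancy screening processes". It names no replacement check.

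**Adverse events.** Section 10.1 describes a questionnaire at the end of each session that asks participants to report "on the severity of symptoms experienced during the stimulation session", plus periodic check-ins during stimulation. Section 10.4 adds: "The study coordinator will follow up within one week of an adverse event".

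**Passive routes.** Section 3.3.2 makes staff reachable by phone and email at any time. Section 8.3.1 withdraws a participant who reports a pregnancy. Section 9.2 has the principal investigator review AEs as they arise and decide on continuation.

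**The concern.** Section 4 separates the visits by at least one week. Several exclusions in section 3.2 can arise in that time, such as a head injury, a seizure, a pregnancy, a new psychiatric or autoimmune diagnosis, or treatment for a new medical disorder. Section 8.3 relies on screening to keep the theoretical seizure risk low, yet the screen is not repeated before the second stimulation. A participant who does not realise that an intervening event matters has no scheduled prompt to mention it.

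The AE record has the same gap. A headache or skin reaction that starts after the participant leaves falls outside the questionnaire's recall period. Section 10.2.1 judges relatedness from timing and from other possible explanations, so the assessor needs onset dates and intervening events that nobody is scheduled to ask for. In a crossover, an event between or after sessions must also be attributed to a condition. The condition given second has no later visit at which a delayed event could come to light.

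At stake are the protocol's own safeguard for the second stimulation and the completeness of the safety record that this pilot passes to a larger study. The biomarker comparison is not the issue.

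**Working it through.** The plan gives no figure to reproduce. The check traces each scheduled contact against the two rules, using sections 3.3.2, 5.1, 5.4.1, 5.4.2, 10.1 and 10.4 and Appendix A.

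| Point in the study | Exclusions checked? | AE question scheduled? | Period it covers |
|---|---|---|---|
| Phone screen | Yes | Not applicable | History to date |
| Session 1, before stimulation | Yes, with drug and pregnancy tests | No | – |
| Session 1, during and after stimulation | No | Check-ins, questionnaire | That stimulation session |
| Between sessions | No; reminder text the day before | Only follow-up of an AE already known | – |
| Session 2, before stimulation | None listed | None listed | – |
| Session 2, during and after stimulation | No | Check-ins, questionnaire | That stimulation session |
| After visit 2 ends | No contact scheduled | Only follow-up of an AE already known | – |

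**Discontinuation rule.** It matters most just before the second stimulation, and that row is empty. The Day 2 questionnaire comes after the second stimulation, so it cannot inform the decision to give it.

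**All-AEs rule.** The solicited questions cover two stimulation sessions. The interval between them and the time after visit 2 are covered by none.

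**The dropped tests are not themselves the defect.** The drug-test exclusion is tied to one occasion: "Failure to pass a urinary drug test at the first session". For pregnancy, section 8.3.1 names self-report as the route. The gap is the absence of any question about the remaining exclusions and about interval events.

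**Exposure.** If all 20 participants attend both visits, there are 20 second stimulations with no listed re-check. At the minimum spacing of 7 days, 20 × 7 = 140 participant-days pass between visits with no scheduled safety question. Both are counts of opportunity. Turning them into missed exclusions or missed AEs would need event rates, which the documents do not give.

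**The case against.** **The rules still work.** A reader might infer that the two rules cannot operate at all. The documents do not support that. Participants can call or write at any time, a reported pregnancy leads to withdrawal, the principal investigator reviews AEs in real time, and staff are with the participant before stimulation. Section 9.3.1 also covers exclusions recognised late, which can be noticed at any contact. What is missing is active ascertainment.

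**Session 2 is not without contact or questions.** A reader might infer that nothing is asked once the second stimulation is over, or that session 2 moves directly to stimulation. The AE questionnaire, PANAS and STAI follow the second stimulation. Before it come electrode placement, a ten-minute resting recording and a saliva sample. The uncovered period begins when the visit ends.

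**Appendix A is not exhaustive.** It omits the EEG recording and the in-session check-ins, both of which are planned. The attached questionnaires, the source-document checklist of section 12.3 and the later appendices are not in the text reviewed, and one of them could hold an interval question. This stands as a caveat. However, eligibility assessment does have its own row in Appendix A, marked for two of three columns, so the Day 2 blank is more than an unlisted item. Section 5.4.2 does not fill it.

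**The consequences are modest.** Participants are healthy adults (18 to 35 in section 3.1), and AEs are neither a primary nor a secondary outcome in section 11.1.1. That limits the weight of the point. It does not remove the mismatch between rules and schedule.

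**Time shares mislead.** It is tempting to express visit hours as a fraction of elapsed time and read the remainder as the share of AEs missed. Safety questions do not span whole visits, and elapsed time is not an event rate.

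**Conclusion.** The point holds as a mismatch between the rules in sections 9.3.1 and 10.2.1 and the schedule in section 5.4.2 and Appendix A. Followed as written, the schedule gives the second stimulation with no listed check of the plan's own discontinuation criterion. Interval and late AEs reach the record only if volunteered.

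The likely number of affected participants is small but cannot be estimated from the documents. The consequence is an avoidable gap in participant protection and an AE record whose solicited part is confined to in-session symptoms. A reader might infer a bias in the AE comparison between tACS and sham. Section 6.2 randomises the order of conditions, so under-recording may touch both, and the documents support no direction.

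The conclusion assumes that Appendix A is read correctly from its column positions, and that no interval question sits in the attachments not supplied. Sections 8.3.1 and 9.3.1 do not conflict on pregnancy. The one-week figure in section 10.4 is a deadline for a known AE and should not be read as an observation window.

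**What to change.** 1. In Appendix A, mark the eligibility row for Day 2. In section 5.4.2, describe it as a verbal run through the existing screening checklist before electrodes are applied.
2. At the same point, ask one open question on symptoms, illness, injury or new medication since session 1, and log the answer with its onset date.
3. For the time after session 2, either add a brief message asking the same question, with timing set by the investigators, or state that AE data end with visit 2 and qualify the all-AEs statement in section 10.2.1 to match.
4. If an interval question already exists in an attachment or checklist, cite it in section 5.4.2 and Appendix A.

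The sponsor should reconcile section 5.4.2 and Appendix A with sections 9.3.1 and 10.2.1. None of this changes who is discontinued. It supplies detection for a rule that the protocol already has.

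The cost is protocol wording, a few minutes per participant at an existing visit and, if that option is taken, at most 20 short messages. Reminder texts are already sent. The downside is small: a few more AEs to record and possibly an occasional participant who does not receive session 2.

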9.3.2 DATA COLLECTION AND FOLLOW-UP FOR WITHDRAWN PARTICIPANTS

We will collect safety data on any participant discontinued because of an AE or SAE. In any case, every effort will be made to undertake protocol-specific follow-up procedures. If an AE has been reported, researchers will help the participant seek the medical care they need and a follow-up will be performed by the PI. In the case of an early withdrawal, the researcher will make a note to file indicating this.

9.4 TERMINATION OF STUDY

If a seizure occurs at the time of a study visit, a temporary hold will be placed over the study and further investigation will ensue. This could lead to stopping the study prematurely or continuing on with further safety measures in place. If two seizures are witnessed during the study visits, the entire study will be stopped prematurely. These individuals would be referred for further medical attention. It is very unlikely that a seizure will occur, given that previous studies using tDCS in patients with depression and schizophrenia have had no seizures occur (Berlim et al., 2013, Brunelin et al., 2012).

The study will also be stopped (at least temporarily) if studies provide evidence that transcranial current stimulation caused brain damage or other harmful effects on subjects, either short-term or long-term. Examples of findings that might trigger a safety review are the number of SAEs overall, the number of occurrences of a particular type of SAE, severe AEs/reactions, or increased frequency of events.

The reasons for stopping the study and asking for further investigation include:

- If a seizure occurs during a study visit, a temporary hold will be placed on the clinical trial

The IRB will also be informed promptly and provided the reason(s) for the termination of suspension of by the investigator, as specified by the applicable regulatory requirement(s).

10 SAFETY & REPORTING

It is important to assess safety over the course of this study. This section describes in detail how safety is assessed, reporting of Adverse Events, Serious Adverse Events, and Unanticipated Problems. This section is a reference for internal use.

10.1 SAFETY PARAMETERS

STIMULATION SIDE EFFECTS. A stimulation adverse effects questionnaire used in previous studies will be administered at the end of each stimulation session. This questionnaire will be used as a safety measure and to collect data on participant experience. The adverse effects questionnaire asks participants to respond on a 4 point Likert scale on the severity of symptoms experienced during the stimulation session (1 = absent, 2 = mild, 3 = moderate, 4 = severe). The side effects listed are headache, neck pain, scalp pain, tingling, itching, ringing/buzzing noise, burning sensation, local redness, sleepiness, trouble concentrating, improved mood, worsening of mood, dizziness, flickering lights, and other (specify). Participants are also asked to rate on a 5 point Likert scale how related they believe the side effects to be to stimulation (1 = no relation, 2 = remote, 3 = possible, 4 = probable, 5 = definite).

In addition to this survey, the study coordinator or research assistant will periodically check in with the participant during the stimulation session to assess side effects.

10.2 METHODS AND TIMING FOR ASSESSING, RECORDING, AND ANALYZING SAFETY PARAMETERS

10.2.1 ADVERSE EVENTS

All AEs, including local and systemic reactions not meeting the criteria for “serious adverse events”, will be captured on the appropriate CRF. In addition, the AE Report Form will be completed by the study coordinator (Appendix B). The AE Report Form includes the following:

- What is known about the therapy
- What is known about previous reported side effects
- If the AE occurred in temporal relation to the therapy
- Whether or not the AE improves or disappears when treatment is stopped
- Whether the AE is worsening of baseline symptoms
- Whether the AE is related to concurrent medical condition or medication use

Once complete, this form will be given to the PI and Co-I, who will review, comment, and sign this form. Completed forms will be placed in the participant’s folder.

In addition, the study coordinator will document any AE occurrence on the AE log (*Appendix D*), which includes information such as the date of the AE, severity, relationship to the treatment (assessed by the PI and Co-I*), actions taken, and outcome(s). The log will be reviewed and initialed by the PI 72 hours after being completed. All AEs occurring during the clinical trial will be documented appropriately regardless of relationship to tACS. All AEs will be followed to adequate resolution and will be graded for severity and relationship to study treatment. Any medical condition noted at the initial session will be considered at baseline and not reported as an AE.

All AEs will be graded for severity using the following guidelines:

- **ASYMPTOMATIC.** The participant is exhibiting no symptoms due to this event; no treatment needed.
- **MILD.** Event results in mild or transient discomfort, not requiring intervention or treatment; does not limit or interfere with daily activities (e.g., insomnia, mild headache)
- **MODERATE.** Event is sufficiently discomforting so as to limit or interfere with daily activities; may require interventional treatment (e.g., fever requiring antipyretic medication). In the case of a moderate AE, the medical advisor may recommend an over the counter medication.
- **SEVERE AND UNDESIRABLE.** Event results in significant symptoms that prevent normal daily activities; may require hospitalization or invasive intervention (e.g., anemia resulting in blood transfusion).

Changes in the severity of an AE will be documented with the Note to File document (Appendix E) and will be filed in the participant's folder.

***Relationship to Study Products:** The PI will determine whether an AE is associated with the study treatment. The event will be labeled associated if the event is temporally related to the administration of a therapy and no other factors can explain the event. The event will be labeled as not associated if the event is temporally independent of the study treatment and can be explained by external factors, such as major life events.

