6.3 SAFETY MEASURES

We will be monitoring the safety of our participants throughout the study with the following measures. These measures are listed below and can be found in the attached documents.

- A. A stimulation adverse effects questionnaire used in previous studies (IRB #14-1622, #14-3285, and #14-0600) will be administered at the end of each stimulation session. This questionnaire will be used as a safety measure and to collect data on participant experience. Please see 10.1 *Safety Parameters* for more information.

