APPENDIX B: AE REPORT FORM

Adverse Effects Report:

Reasons for Report (adverse event, time, date and place of occurrence if available):

1. What do we already know about the therapy?
 - a.
2. What is the temporal relationship of the AE to the study therapy?
 - a.
3. Does the AE improve or disappear when the therapy is stopped?
 - a.
4. Is the AE a worsening of baseline symptom(s)?
 - a.
5. Is the AE a result of an underlying concurrent medical condition(s) or concurrent medication(s)?
 - a.
6. Additional Information provided by research team
 - a.

Research team member signature _____

Date _____

Co-Investigator:

Steps to be taken (if applicable)

Co-I signature

Date _____

PI Comments:

Steps to be taken (if applicable)

PI signature

Date _____

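### The AE form asks about worsening of baseline symptoms, but no step rates the side-effect items before stimulation, so no same-day rating separates symptoms a participant arrived with

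*Combined protocol and SAP*

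**What the plan says.** Section 10.2.1 sets out what the AE Report Form must cover, including "Whether the AE is worsening of baseline symptoms". Appendix B carries this as item 4: "Is the AE a worsening of baseline symptom(s)?"

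The side-effect questionnaire has one stated time point per session. Section 6.3 says that it "will be administered at the end of each stimulation session". Section 10.1 agrees: "A stimulation adverse effects questionnaire used in previous studies will be administered at the end of each stimulation session". The session 1 description under section 5.2 puts it in order: "After the stimulation, the participant will complete the stimulation adverse effects questionnaire, and will then provide a final saliva sample". Session 2 follows the same timeline. Appendix A has a single "Stimulation Questionnaire" row, placed after the stimulation row and ticked once for each stimulation day.

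Section 10.1 describes two ratings on the questionnaire. One is a four-point scale "on the severity of symptoms experienced during the stimulation session". The other is a five-point scale for "how related they believe the side effects to be to stimulation", whose lowest point is no relation. The list has 15 entries, counting the free-text one. Among them are headache, neck pain, sleepiness and trouble concentrating.

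**The concern.** A form that asks whether an event is worse than baseline needs a baseline. Several listed symptoms are ones that healthy adults may have on any day. If nobody rates them before the current is switched on, a later report of, say, a mild headache could mean a new symptom, a worse one, or the one the participant walked in with.

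Two things depend on the distinction. One is the call on an individual event. Under the relationship rule in section 10.2.1, the PI labels an event associated when it is temporally related to treatment and nothing else explains it. An unrecorded symptom that predates stimulation is exactly the kind of other explanation that rule needs to see. The second is the tolerability record. The trial is a pilot meant to inform a larger study (sections 4 and 11.1.2), and side-effect rates taken from it will include background symptoms in an unknown proportion.

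**Working it through.** The documents give no side-effect rate or background symptom rate, so there is no planned figure to reproduce. The check is a comparison of sections, followed by a bounded illustration.

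**Step 1. Is there a same-day baseline anywhere else?**
- Telephone screening (section 6.1) collects medical and medication history. This is a written record, but not a symptom rating on the day.
- Section 7.3 has participants complete questionnaires before the electrodes are fitted, without naming them. Appendix A lists the Day 1 baseline scales as PSS, CD-RISQ and PSQI; none is this symptom list. PANAS and STAI are final questionnaires.
- Section 10.2.1 treats a medical condition noted at the initial session as baseline and not as an AE. No step prompts for the questionnaire's symptoms at that session, and no matching rule covers session 2.
- Staff check-ins (sections 8.2.2, 8.3 and 10.1) take place during stimulation, not before it.
- On Day 2, Appendix A lists nothing before stimulation except the saliva sample. Section 4 separates the visits by at least a week, so anything noted at session 1 is old by then.

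No step rates the items before stimulation at either session, and session 2 has the least information.

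**Step 2. How many reports could be background?**
Inputs: n = 20 participants (section 3); b = share who arrive with a given common symptom. The value of b is an assumption, taken over 10% to 40%.

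Expected number per item per session = n × b:
- b = 10%: 20 × 0.10 = 2
- b = 20%: 20 × 0.20 = 4
- b = 30%: 20 × 0.30 = 6
- b = 40%: 20 × 0.40 = 8

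These participants could report the symptom without stimulation having caused it. The count does not say how many would be attributed to stimulation.

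**Step 3. What happens to an active-versus-sham comparison?**
Let pA and pS be the chances that someone without the symptom develops it in the active and sham sessions, with b the same before both. The chance of any report is b + (1 − b)pA under active and b + (1 − b)pS under sham. The difference is (1 − b)(pA − pS).

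Equal background therefore creates no false difference on average. It raises both absolute rates and shrinks a true difference by the factor 1 − b: 0.9, 0.8, 0.7 and 0.6 for b = 10%, 20%, 30% and 40%. Section 11 specifies no active-versus-sham analysis of the questionnaire, so the absolute rates are the more exposed quantity.

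**The case against.** A reader might infer that every symptom present on arrival is scored as a stimulation effect. The documents do not support that. Section 10.1 separates severity from attribution, and a participant who came in sleepy can mark no relation. The PI decides association, and Appendix B also asks about timing and about concurrent conditions or medication. Under section 8.3, staff discuss moderate-to-severe ratings with the participant and note the response, and that conversation can establish which came first.

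A reader might also infer that item 4 can be answered only from memory. That goes too far: screening history and conditions noted at session 1 are on record. Item 4 is a free-text prompt, and nothing requires a numeric pre-score.

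Further points on this side are fair. Each participant has a sham session (section 6.2), which balances background symptoms on average. Tingling, burning, local redness and flickering lights are less likely to be brought from home. Improved mood and worsening of mood are already change items, so subtracting a pre-rating makes no sense for them. The questionnaire is an attachment not included in the documents reviewed, so it may ask about prior presence, although section 10.1 describes no such item.

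What does not stand is that these safeguards fill the gap. The relatedness rating is a belief given afterwards, not a reference value. The discussion in section 8.3 is prompted by moderate-to-severe ratings, so a mild symptom may never reach it. The sham session helps averages, not an individual event.

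**Conclusion.** The gap is real and small. The AE form calls for a comparison with baseline symptoms, and the schedule collects no same-day rating of the questionnaire's items at either session. Symptoms already present can be recorded, and possibly judged associated, with nothing measured to separate them. Existing safeguards reduce the problem without removing it.

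On size, 2 to 8 of 20 participants per common item per session is an upper illustration of background reports, not a count of misattributed events. It rests wholly on the assumed 10% to 40%. The shrinkage factor in the active-versus-sham difference also assumes equal background before both sessions.

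It would be wrong to infer that the trial's main conclusions are at risk. The primary outcomes are salivary biomarkers and the secondary outcomes are EEG changes (section 11.1.1), and neither uses the questionnaire. What is affected is attribution of individual events and the tolerability description carried into a larger trial. Label: cheap improvement.

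**What to change.** Give the severity column of the existing questionnaire, without the two mood-change items, after electrode placement and before stimulation, at the same point in both sessions. That leaves 15 − 2 = 13 entries. Add the row to Appendix A for both stimulation days and to the session descriptions under section 5.2.

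In section 11, state that post-stimulation ratings and the pre-to-post change will be reported for active and sham. Both conditions are needed because change alone does not isolate stimulation: a participant may become sleepy during a 40-minute nature film in either session. Use the two ratings to inform item 4 of the AE Report Form.

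Keep recording all AEs, and leave the discussion, PI-contact and stopping rules as they are; the pre-rating adds information and does not filter reports.

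The cost is about two minutes per session (an estimate) on a form already in use. The downside is a slight chance that asking beforehand primes participants to notice symptoms, which should be similar in both conditions.
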